## 5.0 Statistical Analysis

A two-way ANOVA will be the first step of analysis to determine the influence of the BiPAP systems on the NPPV. Regional distribution of tidal volume will be analyzed using four ventral to dorsal regions of interest (ROI) by EIT. The relative distribution of tidal volume between regions will be displayed as a percentage. Regional change in end-expiratory lung impedance (EELI) will be similarly expressed as a percent for each ROI. These parameters will be treated as functions of each individual step outlined in 4.6, with particular attention paid to the pressure support and PEEP. Values will be presented as mean  $\pm$  standard deviation and initial comparisons will be made using paired *t*-tests against baseline. Given the factorial design of experiment, if further analysis becomes warranted, a multivariate ANOVA will be utilized to determine the time, pressure, and total tidal volume relationship to relative distribution of tidal volume within the regions of interest. Potential confounding parameters such as patient size, weight, and health status will be screened in a similar manner.

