## **4.0 Study Procedures**

4.1 Written informed consent will be obtained on all subjects prior to enrollment in the study and before any research procedures are performed. Subjects can withdraw from the study at any time.

4.2 Subjects will undergo testing by applying NPPV via 2 different BiPAP devices that are currently used in standard of care for patients at the University of Michigan Health System. The decision of which device to begin with will be determined by random allocation of a coin toss.

4.3 BiPAP Systems:

4.3.1 The Resironics V-60 (Phillips, Carlsbad CA) device is continuous high flow, blower type of generator.

4.3.2 The Drager V-500 (Drager Medical, Lubeck, Germany) is our primary critical care ventilator that has a specific NPPV mode.

- 4.4 EIT System: The Drager PulmoVista 500 EIT system (Drager Medical, Lubeck, Germany) consists of an electrode belt connected to the EIT monitor. Before using the system it will be reviewed and approved for use by our Biomedical Department.
- 4.5 Subjects will be placed in the supine position. This position will be maintained for the entire procedure. An electrode belt will be placed on the subject at the 5th intercostal space and connected to the EIT monitor. Prior to initiating a study session, the EIT system will be calibrated per manufacturer's instruction.
- 4.6 Each study device will be applied in the following manner:
  - 4.6.1 Four steps (series of device setting changes) will be applied, as such:
    - 4.6.1.1 A baseline will be established breathing without the NPPV mask attached
    - 4.6.1.2 Following mask attachment, a pressure support of 0 cm H2O and PEEP of 5 cm H2O will be applied, then
    - 4.6.1.3 A pressure support of 5 cm H2O and PEEP of 5 cm H2O, then
    - 4.6.1.4 A pressure support of 5 cm H2O and PEEP of 10 cm H2O.
  - 4.6.2 Each step will consist of a 5-minute stabilization period, and then readings will be taken over the next two minutes before proceeding to the next step.
  - 4.6.3 Following all four steps with the initial device, the second device will be applied and steps 1-4 repeated.
- 4.7 Primary Outcomes: Global Tidal Variation (see figures 4-6)
- 4.8 Secondary Outcomes:
  - 4.8.1 Regional Tidal Variations
  - 4.8.2 Global and Regional changes in End-Expiratory Lung Impedance (EELI)
- 4.9 Exploratory Outcomes:

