## 7.0 Benefits

There will be no direct benefit to the study subjects. This research will 1) provide an opportunity to learn the EIT system in a nonclinical application on healthy volunteers

before using it in a clinical protocol, and 2) allow comparison of NPPV systems that are routinely used clinically to hopefully show equivalence in important measures.

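### Section 5.0 plans the device comparison as a two-way ANOVA with no stated subject term, although all 20 subjects are tested on both devices at every step; run literally, its error term is wrong.

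*Combined protocol and SAP*

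**What the plan says.** Sections 3.1, 4.2 and 4.6 describe a fully within-subject design. Twenty healthy volunteers are each tested on two BiPAP devices, and the order is randomised: "The decision of which device to begin with will be determined by random allocation of a coin toss". Each device is taken through four steps. The first has no device acting: "A baseline will be established breathing without the NPPV mask attached". The other three are pressure settings with the mask on. Section 4.6.3 then says: "Following all four steps with the initial device, the second device will be applied and steps 1-4 repeated". Each subject therefore contributes eight correlated conditions.

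For the device comparison, section 5.0 says: "A two-way ANOVA will be the first step of analysis to determine the influence of the BiPAP systems on the NPPV". It does not name the two factors, a subject term, a repeated-measures structure or an error term. Pairing appears once: "initial comparisons will be made using paired *t*-tests against baseline". Section 5.0 calls the design factorial, and the multivariate ANOVA it holds in reserve also has no stated subject term. On the steps it says: "These parameters will be treated as functions of each individual step outlined in 4.6". That takes in the no-mask step, and nothing says whether this step enters the device effect.

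The primary outcome, global Tidal Variation (4.7), is not defined as a raw value or as a change. The EELI outcomes (4.8.2) are defined as changes.

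**The concern.** When every subject uses both devices, stable differences between subjects cancel from the device comparison. They belong in neither the device difference nor its error term. An ANOVA that treats all values as independent leaves them in the error term, and it gives too little weight to variation in how individual subjects respond to the two devices. These two faults push the test in opposite directions, so its error rate depends on variances that the plan does not give.

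The direction matters. Section 2.0 hypothesises no difference between devices, and section 7.0 says the study will "allow comparison of NPPV systems that are routinely used clinically to hopefully show equivalence in important measures". A test that is too conservative misses real differences and so favours the hoped-for result. A test that is too liberal reports device differences that do not exist.

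**Working it through.** **Inputs from the documents.** 20 subjects (3.1), 2 devices (4.2), 4 steps per device of which 3 are mask-on (4.6.1). The plan gives no significance level, power, effect size or variance, so there is no figure of its own to reproduce.

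**Assumptions.** Two-sided 5% level and total variance 1, split into Vs (between-subject), Vsd (subject-by-device, including subject-by-period, because each device is used in one period), Vsp (subject-by-step) and Ve (residual). Splits below are written Vs/Vsd/Vsp/Ve.

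**Degrees of freedom.** A literal device × step ANOVA on the mask-on steps uses 20 × 2 × 3 = 120 values in 6 cells, with 120 − 6 = 114 error df. With step 1 included it is 160 − 8 = 152. The within-subject device test has 20 − 1 = 19.

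**Raw values, three mask-on steps.**
- Variance the literal ANOVA assumes for the device difference: 2(Vs+Vsd+Vsp+Ve)/60.
- True variance: (2Vsd + 2Ve/3)/20.
- Ratio, assumed to true: (Vs+Vsd+Vsp+Ve)/(3Vsd+Ve).
- Approximate type I error: 2 × (1 − Φ(1.96 × √ratio)).

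The test is conservative when Vs+Vsp > 2Vsd and anti-conservative when the reverse holds. The simulations used 40,000 trials per split. The effect was set so that the paired test on the mean of three steps has 80% power (noncentrality 2.954).

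| Vs/Vsd/Vsp/Ve | Ratio | Type I, formula | Type I, simulated | Power, literal ANOVA |
|---|---|---|---|---|
| 0.3/0/0/0.7 | 1/0.7 = 1.43 | 1.9% | 1.9% | 72% |
| 0.5/0/0/0.5 | 1/0.5 = 2.00 | 0.6% | 0.7% | 56% |
| 0.7/0/0/0.3 | 1/0.3 = 3.33 | 0.03% | 0.1% | 29% |
| 0.4/0.2/0/0.4 | 1/1.0 = 1.00 | 5.0% | 5.3% | 83% |
| 0.1/0.4/0/0.5 | 1/1.7 = 0.59 | 13.3% | 13.3% | 93% |

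The last power figure is no advantage, because it comes with a 13% false-positive rate. The within-subject test holds 4.8% to 5.2% in all 13 splits tried.

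**Four steps, raw values.** Including step 1 leaves the same pattern: 2.3%, 0.8% and 0.1% at between-subject shares of 0.3, 0.5 and 0.7. With subject-by-device variance present at all four steps, type I error is 12% at 0.3/0.3/0/0.4 and 20% at 0.2/0.5/0/0.3, against 9% and 15% on three steps.

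**Change from the device-specific baseline.** With Vsd = Vsp = 0, the ratio is 2Ve/4Ve = 0.5, and type I error is about 16% to 17%. At 0.2/0/0.6/0.2 the ratio is (2×0.6 + 2×0.2)/(4×0.2) = 2, and type I error is about 0.7%. The test can therefore be off in either direction on this scale too.

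When Vsd is above zero, the answer depends on whether that variance is also present in the no-mask baseline. If it acts only with the mask on, the ratio is (Vsd+2Vsp+2Ve)/(3Vsd+4Ve). If it is also in the baseline it cancels, and the ratio is (2Vsp+2Ve)/(4Ve). At 0.2/0.15/0.35/0.3 these are 1.45/1.65 = 0.88 (about 7%) and 1.30/1.20 = 1.08 (between 4% and 5%). The direction changes, so no single break-even can be given.

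**Subject as an additive block only.** This is not enough. With three steps, Vsd of 0.1 to 0.5 and Vsp = 0, type I error is 16% to 26%. The error term itself has to be stated.

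**The case against.** The strongest reply is that the model is unspecified, not wrong. Two-way ANOVA may be shorthand for a two-way repeated-measures ANOVA, or for device by subject, and the same paragraph plans paired t-tests, so the authors know the data are paired. This stands. A reader might infer that the plan commits to an unpaired device comparison, but the text does not support that. It leaves the model open, and one natural reading is invalid.

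A second reply is that every magnitude is assumed. This also stands. A reader might infer that the test is always too conservative and so biased towards finding no difference. That holds only for some variance splits, and the documents do not say which apply here.

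A third reply is that the scale is not wholly missing. Section 5.0 expresses the regional split of tidal volume and the regional EELI change in percent. That is correct, and the gap is mainly the primary outcome. The variance model above was not built for percentages.

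Finally, this is an initial project in 20 healthy volunteers, and the wording can be settled before analysis. That bears on how serious the point is, but it does not remove the need to name the error term.

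**Conclusion.** The point holds as a gap in specification that should be closed before analysis. The design is within-subject, the device test is not stated to be, and a literal run gives a wrong error rate. On raw values with three mask-on steps, type I error is about 0.1% to 1.9% where between-subject variance is the only subject component, with power of 29% to 72% in place of 80%. It is about 13% where subject-by-device variance is large. On change scores it is about 16% to 17% with no subject-by-device or subject-by-step variance, and it can fall well below 5% when subject-by-step variance is large. All of this rests on assumed variances and an assumed 5% level, so no figure is established for this trial.

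A reader might also infer that a correct error term would let the study show equivalence. It would not: a non-significant difference from a valid test is still not evidence of equivalence.

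**What to change.** Replace the ANOVA sentence in section 5.0 with:

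> Device effects will be tested within subject by a two-way repeated-measures ANOVA (device × pressure step, both within subject) on the three mask-on steps, with device tested against subject-by-device and device-by-step against subject-by-device-by-step (with a sphericity correction), or by an equivalent mixed model with random subject, subject-by-device and subject-by-step terms. Paired device differences will be reported per step with 95% confidence intervals. The no-mask step 1 is not averaged into the device effect.

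The device-by-step test serves the second hypothesis in section 2.0, that the shift with pressure is similar between devices. Also state whether global Tidal Variation is analysed as a raw value or as a change.

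Leaving step 1 out of the device effect preserves power. Averaging it in lowers the within-subject test from 80% to about 68% when Vsd = 0, or to 74% to 77% when Vsd is 0.1 to 0.4.

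A period term is optional. It costs about 2 to 3 points of power if there is no period effect. If a period effect shifts the paired difference by half its standard deviation (assumed), the term raises power from 70–71% to 77–78%.

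The mixed-model form is slightly conservative when Vsd = 0: type I error is 3.8% to 4.2%, calculated with a period term included. With Vsd of 0.1 or more it matches the repeated-measures test.

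The cost is SAP wording only, with no added data or visits.

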  - 4.9.1 A pneumotachometer (NM3 monitor, Phillips Healthcare, Andover MA), will be placed between the mask and inspiratory hose and the following measurements obtained: respiratory rate, tidal volume, peak inspiratory

pressure, PEEP. A pulse oximeter (RAD8, Masimo, Irvine CA) will provide SpO2 and heart rate.

- 4.9.2 Change in regional and global distribution in subjects with a BMI less than or greater than 25 kg/m^2
- 4.9.3 Change in global and regional distribution for subjects at 0 degrees, 45 degrees, and 90 degrees' body positions.

4.10 In addition to device testing, baseline demographics such as age and gender will be recorded for each subject.

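### The only pairwise tests named in 5.0 compare each step with no-mask breathing, so they estimate mask plus pressure and do not test the second hypothesis about increasing pressure

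*Combined protocol and SAP*

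**What the plan says.** Section 2.0 has two parts. The first is that the devices do not differ at the same settings. The second is that ventilation moves from ventral to dorsal regions as NPPV pressure is raised, and does so similarly with both devices.

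Section 4.6.1 gives four steps per device:

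- Step 1: "A baseline will be established breathing without the NPPV mask attached".
- Step 2: "Following mask attachment, a pressure support of 0 cm H 2 O and PEEP of 5 cm H 2 O will be applied".
- Step 3: pressure support rises to 5 cm H2O, PEEP stays at 5.
- Step 4: PEEP rises to 10 cm H2O, pressure support stays at 5.

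On timing, 4.6.2 says: "Each step will consist of a 5-minute stabilization period, and then readings will be taken over the next two minutes". On the second device, 4.6.3 says: "Following all four steps with the initial device, the second device will be applied and steps 1-4 repeated".

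Section 5.0 begins: "A two-way ANOVA will be the first step of analysis to determine the influence of the BiPAP systems on the NPPV". It says outcomes will be examined by step, "with particular attention paid to the pressure support and PEEP", and then that "initial comparisons will be made using paired *t*-tests against baseline". A multivariate ANOVA that includes pressure is to be used only if further analysis is thought warranted. No comparison between two mask-on steps is named.

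**The concern.** The second hypothesis is about what happens as pressure goes up. The reference for every named pairwise test is a state that differs from the later steps in two ways: no mask and no applied pressure. Step 2 changes both at once, and no step has the mask on at zero pressure.

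If wearing the mask alone alters the distribution of tidal ventilation, all three baseline tests pick that up. A significant result could then be reported as a response to pressure when pressure did nothing. The two comparisons in which the mask is on throughout and one setting changes are already in the planned readings. Unless they are named in advance, choosing them becomes a decision made after seeing the data.

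**Working it through.** **Plan's own figure.** There is none to reproduce. Section 3.1 gives 20 volunteers. The documents state no significance level, SD, effect size or power.

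**Step 1: what each difference estimates** (settings from 4.6.1). Write M for the mask effect and treat it as constant once the mask is on.

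| Difference | Expected value | Named in 5.0? |
|---|---|---|
| Step 2 − step 1 | M + (PEEP 0→5) | yes |
| Step 3 − step 1 | M + (PEEP 0→5) + (PS 0→5) | yes |
| Step 4 − step 1 | M + (PEEP 0→10) + (PS 0→5) | yes |
| Step 3 − step 2 | PS 0→5 at PEEP 5 | no |
| Step 4 − step 3 | PEEP 5→10 at PS 5 | no |

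M is in all three named tests and cancels from the two that are not named. M and the first PEEP increase can be separated only by assuming that PEEP 0→5 has the same effect as PEEP 5→10. In that case M = (step 2 − step 1) − (step 4 − step 3).

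**Step 2: how much a mask-only effect would matter.** Assumptions: n = 20, one device, two-sided 0.05, no pressure effect, no drift, and mask effect δ in SDs of the paired difference. The paired t statistic is noncentral t with 20 − 1 = 19 df and noncentrality δ√20. Power is P(|T| > t(0.975, 19)).

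| δ | Noncentrality δ√20 | Each baseline test significant | Step 3 − 2 or step 4 − 3 significant |
|---|---|---|---|
| 0.25 | 1.12 | 19% | 5% |
| 0.5 | 2.24 | 56% | 5% |
| 0.75 | 3.35 | 89% | 5% |

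The last column follows from the cancellation of M, and simulation agrees (0.049 to 0.052).

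**Step 3: what the mask-on contrasts do not remove.** The steps always run in the same ascending order, with readings 5 + 2 = 7 minutes apart. Take the four steps with columns for intercept, mask, pressure support and PEEP: the rank is 4. Add a linear time column and the rank is still 4, now for 5 columns. Pressure and time therefore cannot be separated within a device run.

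Suppose there is no mask effect and no pressure effect, but a drift of d SD of the paired difference per step. Each adjacent contrast then has expected value d, so the same formula gives 19% at d = 0.25 and 56% at d = 0.5. The baseline tests carry the drift as well, and more of it later on: d, 2d and 3d for steps 2, 3 and 4. At d = 0.25 these are 0.25, 0.5 and 0.75 SD, or 19%, 56% and 89% by the table above.

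**The case against.** **The plan is not silent on pressure.** The t-tests are only initial comparisons. Section 5.0 also has a two-way ANOVA, a stated interest in pressure support and PEEP, and a multivariate ANOVA that includes pressure. Device and step are crossed in 4.6, so device-by-step is a natural reading of two-way. A reader might infer that 5.0 has no analysis of pressure at all, and the text does not support that. What remains is that the ANOVA's stated purpose is the device effect and its levels are not given. An overall step effect that includes step 1 would still contain the mask, and the multivariate ANOVA has no stated trigger.

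**Comparison with baseline is a valid question.** Section 1.0 describes noninvasive ventilation as delivered through a face mask or similar interface, so step minus baseline estimates NPPV by mask against none. This stands. The tests are not invalid; they answer a different question from the second hypothesis.

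**The data are not lost.** Any mask-on contrast is the difference of two baseline differences from the same run. This also stands. It limits the fault to what is pre-specified.

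**The proposed contrasts have their own weakness.** A reader might infer that step 3 minus step 2 and step 4 minus step 3 isolate pressure. They do not, because the fixed order leaves time mixed with pressure. Their 5% error rate rests on no drift and a constant mask effect.

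**The size is hypothetical, and the affected outcome is secondary.** No document gives a mask effect. Regional tidal variation is a secondary outcome (4.8.1) in a 20-volunteer study meant in part for learning the system (7.0). Both statements are fair and limit the weight of the point.

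**Conclusion.** The point holds in this form: the named pairwise tests estimate mask plus pressure, and 5.0 names no unconditional test that clearly addresses increasing pressure. That follows from the step definitions alone and needs no assumption about size.

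The size is unknown. The 19%, 56% and 89% figures rest on assumed mask effects, an assumed two-sided 0.05 level, no pressure effect and no drift. They show how far a baseline test could mislead about pressure, not how far it will.

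A reader might also infer that the comparison between devices is biased. The documents do not support this. Both devices are applied by mask through the same four steps, so the mask is common to both and does not by itself bias the device difference in the first hypothesis.

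The change is worth making because the second hypothesis is half of 2.0 and the better contrasts use readings already planned.

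**What to change.** Amend 5.0 as follows.

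1. **Pressure hypothesis.** Test it with step 3 minus step 2 (pressure support 0 to 5 at PEEP 5) and step 4 minus step 3 (PEEP 5 to 10 at pressure support 5). Use the dorsal share of tidal variation, stating which of the four regions count as dorsal. Average over devices, and give the device difference in each contrast, all with 95% confidence intervals.
2. **Device comparison.** State the ANOVA levels. Make it a within-subject device-by-step analysis on the mask-on steps 2-4, with Global Tidal Variation first.
3. **Baseline tests.** Keep them, but label and interpret them as 'mask plus pressure'.
4. **Limits to state.** The mask-on contrasts remove a constant mask effect but remain confounded with time, because the steps run in one fixed ascending order. The first increase, from no mask to PEEP 5, cannot be separated from the mask.

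The cost is SAP wording and slightly more analysis work. No new readings or subjects are needed and no planned test is removed. The confounding with time is disclosed by this change, not cured.

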## **2.0 Hypothesis**

We hypothesize that the distribution of ventilation and EELV in healthy adult subjects will not be different when NPPV is applied via different devices set to identical pressure settings. Also, when applying increasing NPPV pressures, the distribution of ventilation will shift from the ventral to dorsal regions and be similar between devices.

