## **3.0 Subject Selection and Enrollment**

3.1 Subjects: Twenty adult healthy volunteers will be recruited for this study. They will be solicited from within the University of Michigan Health System (e.g. students, staff, and employees). No financial incentive will be provided.

3.2 Inclusion Criteria:

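### The fixed ascending step order does not let the plan separate time from pressure, so step effects should be reported as setting plus elapsed time

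*Combined protocol and SAP*

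**What the plan says.** The second hypothesis (section 2.0) predicts that "when applying increasing NPPV pressures, the distribution of ventilation will shift from the ventral to dorsal regions", similarly for both devices.

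Section 4.6.1 gives one sequence: an off-mask baseline ("A baseline will be established breathing without the NPPV mask attached"), then pressure support 0 with PEEP 5, then 5 with 5, then 5 with 10 cm H2O. On timing, section 4.6.2 says: "Each step will consist of a 5-minute stabilization period, and then readings will be taken over the next two minutes". Section 4.6.3 adds that "the second device will be applied and steps 1-4 repeated". The one randomised element is in section 4.2: "The decision of which device to begin with will be determined by random allocation of a coin toss". No step is reordered, reversed or repeated within a run.

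Section 5.0 starts with a two-way ANOVA for the influence of the BiPAP systems and makes its initial comparisons by paired t-tests against baseline. It then says: "Given the factorial design of experiment, if further analysis becomes warranted, a multivariate ANOVA will be utilized to determine the time, pressure". The sentence goes on to list total tidal volume, and relates all three to regional distribution. It does not define time, and it gives no order, period or drift term. The confounders it lists are patient size, weight and health status.

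**The concern.** The second hypothesis concerns a trend across the steps of a run. In every run, later steps are also higher-pressure steps. Anything that moves regional impedance steadily with time, such as a slow change while lying supine (section 4.5 keeps that position throughout) or signal drift under the belt, would have the same sign in all 40 runs (20 subjects x 2 devices) and would not average out.

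If such a shift ran from ventral to dorsal, it would look like the predicted effect of pressure. If it ran the other way, it could hide a real one. The first-line paired t-tests are exposed because baseline always comes first. The conditional multivariate ANOVA is exposed because its wording promises a separation that the schedule does not provide. What is at stake is the interpretation of the pressure hypothesis, which rests mainly on the regional (secondary) outcomes, and of any step effect on the other outcomes.

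**Working it through.** **Inputs.** Twenty subjects, each on both devices (sections 3.1 and 4.2). Four steps of 5 + 2 = 7 minutes (4.6.2), so 4 x 7 = 28 minutes per run and 56 minutes of steps in total. The total procedure is put at 90-120 minutes (6.0). Alpha, SDs and drift size are not stated, so two-sided 5% and a range of drift are assumed. The plan has no power or sample-size figure to reproduce.

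**1. Order against pressure.** Steps 1 to 4 have pressure support + PEEP of 0, 5, 10 and 15. The correlation of this sum with step order is 1.000; for PEEP alone it is 0.949 and for pressure support alone 0.894.

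**2. What can be estimated.** A model separates its effects only if its design matrix has as many independent columns as it has columns. On the nominal schedule, with 20 subjects and an assumed 10/10 split of device order:

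| Model | Rank | Columns |
|---|---|---|
| subject + device + step | 24 | 24 |
| + within-run time | 24 | 25 |
| + session time (both runs on one clock) | 25 | 25 |
| + period + session time | 25 | 26 |

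Within a run, time is 7 x (step - 1), so it adds nothing to step. A straight-line drift over the whole session can be estimated from run 2 versus run 1, but only if there is no period or carry-over effect. With a period term that is lost, because time from the start is then 7 x (step - 1) + 28 x (period - 1).

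This last identity assumes that no time passes between runs. Section 6.0 leaves 90 - 56 = 34 to 120 - 56 = 64 minutes for set-up, changeover and anything else. In a model of subject + step + period + time, a fixed gap gives rank 24 of 25. If changeover varies between subjects (5-30 minutes assumed), it gives 25 of 25. Time is then identifiable, but only weakly and through unplanned variation.

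**3. Bias.** Set the true pressure effect to zero and let drift be 1 unit per step. Subject + device + step then estimates 1, 2 and 3 units for steps 2, 3 and 4 against baseline, and adding a period term does not change this. The step 3 minus 2 and step 4 minus 3 contrasts each carry 1 unit. The device estimate is 0 with balanced device order. Drift that restarts with each run still gives 1, 2, 3 when session time is in the model.

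**4. Size.** For a paired t-test with n = 20 (19 df, critical value 2.093), the noncentrality is d x sqrt(20), where d is drift in SDs of the paired difference. An adjacent-step contrast carries d/3 if drift is linear; the same SD is assumed for both contrasts.

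| Drift, baseline to step 4 (assumed) | Step 4 vs baseline: noncentrality, P(significant) | Adjacent steps: noncentrality, P(significant) |
|---|---|---|
| 0.25 SD | 1.118, 19% | 0.373, 6% |
| 0.50 SD | 2.236, 56% | 0.745, 11% |
| 0.75 SD | 3.354, 89% | 1.118, 19% |

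The nominal rate is 5%.

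**The case against.** Much can be said for the plan.

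- **The factorial wording has a valid reading.** The paragraph opens with a two-way ANOVA on BiPAP system, and device by step is a complete 2 x 4 crossing. A reader might infer that the design is not factorial at all. It is, for device and step; the wording goes too far only where it supports time and pressure. That time is left undefined is part of the same defect.
- **Pressure support and PEEP.** A reader might add that only three of the four combinations on the mask are run, so their interaction cannot be estimated. That is true, but section 5.0 plans no such interaction and treats outcomes as functions of the individual step.
- **Time is not strictly inestimable.** A reader might infer that it can never be estimated. That needs a zero or constant changeover, which the protocol does not state.
- **Exposure is limited.** Baseline is taken again at the start of each run, so a comparison with that run's own baseline spans about 3 x 7 = 21 minutes. The step 4 versus baseline contrast also includes putting on the mask, so it is not a clean pressure contrast even without drift.
- **The stabilisation period.** Five minutes per step deals with settling after each change, not with slow change over the session.
- **The multivariate ANOVA is conditional.** It is, but the planned paired t-tests have the same exposure without it.

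These points narrow the concern. They do not restore the claim that time and pressure relationships can be separately determined.

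**Conclusion.** The point holds in limited form. As written, section 5.0 promises a separation of time and pressure that section 4.6 does not support without assumptions the plan never states: no period or carry-over effect, or usable variation in changeover time. The step results support a combined effect of setting and elapsed time, and the second hypothesis cannot be confirmed from them as a pure pressure effect.

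The size depends on a drift that the documents do not give. The 19%, 56% and 89% are illustrations for the most exposed contrast and should not be read as the trial's expected error rate; for adjacent steps the same assumptions give about 6%, 11% and 19%. Nothing here shows that drift is present.

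A reader might also infer that the device comparison is compromised. The documents do not support that: both devices follow the same steps and the starting device is randomised, so same-step comparisons are largely protected. The protection is complete in the calculation only with balanced device order, which a coin toss does not guarantee.

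**What to change.** Leave the step schedule as it is and change section 5.0:

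1. Limit the factorial description to device by step, and remove the claim to determine time separately from pressure.
2. Report step effects, including the step 3 minus 2 and step 4 minus 3 contrasts, as combined effects of setting and elapsed time.
3. Report the difference between the two off-mask baselines (run 2 minus run 1, at the actual recorded times) with a confidence interval, as a descriptive drift check. State that it includes any carry-over from the first run and cannot detect drift that restarts with each run.

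Do not subtract 7/28 of the baseline difference per step, and do not make the pressure claim depend on such a correction. It would assume that the whole difference between runs is linear drift with no changeover time, and it could remove a true effect or pass a false one.

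The cost is a few lines of wording, one descriptive estimate from readings already scheduled, and a record of when they were taken. The downside is a slightly more cautious conclusion about pressure.
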